7.5 Follow-up of Adverse Events

All adverse events will be followed with appropriate medical management until resolved. Patients removed from study for unacceptable adverse events will be followed until resolution or stabilization of the adverse event. For selected adverse events for which administration of the investigational drug was stopped, a re-challenge of the subject with the investigational drug may be conducted if considered both safe and ethical by the Investigator.

7.6 Expedited Reporting

Reporting to the Data and Safety Monitoring Committee

If a death occurs during the treatment phase of the study or within 30 days after the last administration of the study drug(s) and it is determined to be related either to the study drug(s) or to a study procedure, the Investigator or his/her designee must notify the DSMC Chair (or qualified alternate) within 1 business day of knowledge of the event. The contact may be by phone or e-mail.

Reporting to UCSF Committee on Human Research (Institutional Review Board)

The Principal Investigator must report events meeting the UCSF CHR definition of “Unanticipated Problem” (UP) and the San Francisco VA Medical Center within 5 business days of his/her awareness of the event.

Expedited Reporting to the Food and Drug Administration

If the study is being conducted under an IND, the Sponsor-Investigator is responsible for determining whether or not the suspected adverse reaction meets the criteria for expedited reporting in accordance with Federal Regulations (21 CFR §312.32).

The Investigator must report in an IND safety report any suspected adverse reaction that is both serious and unexpected. The Sponsor-Investigator needs to ensure that the event meets all three definitions:

- Suspected adverse reaction (as defined in 6.1.30)
- Unexpected (as defined in 0)
- Serious (as defined in 6.1.5)

If the adverse event does not meet all three of the definitions, it should not be submitted as an expedited IND safety report.

The timeline for submitting an IND safety report to FDA is no later than **15 calendar days** after the Investigator determines that the suspected adverse reaction qualifies for reporting (21 CFR 312.32(c)(1)).

Any unexpected fatal or life-threatening suspected adverse reaction will be reported to FDA no later than **7 calendar days** after the Investigator's initial receipt of the information (21 CFR 312.32(c)(2)).

Any relevant additional information that pertains to a previously submitted IND safety report will be submitted to FDA as a Follow-up IND Safety Report without delay, as soon as the information is available (21 CFR 312.32(d)(2)).

8 Statistical Considerations and Evaluation of Results

8.1 Study Endpoints

Per patient and per region ⁶⁸Ga-PSMA-11 sensitivity for the detection of prostate cancer recurrence .

8.1.1 Randomization

There will be no randomization performed.

8.1.2 Blinding

- For primary endpoint analysis of ⁶⁸Ga-PSMA-11 PET imaging studies central readers will be fully blinded to clinical information and any conventional imaging results. Central readers will have access to the concomitant CT or MRI used for attenuation purposes.
- For local interpretation of ⁶⁸Ga-PSMA-11 PET imaging studies, local readers will be unblinded to both clinical information and other conventional imaging data.
- For local interpretation of conventional imaging follow-up images 3-12 months post ⁶⁸Ga-PSMA-11 PET scan, local readers will be unblinded to all results and will be specifically informed of the location of ⁶⁸Ga-PSMA-11 PET positive lesions so that follow-up measurements may be performed on these lesions.

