- i) Lymph nodes will be considered positive if the ^{68}Ga -PSMA-11 uptake is focal and greater than blood pool (adjacent or mediastinal blood pool).
 - (1) Lymph nodes will be classified further by region: pelvic, retroperitoneal, thoracic, other. Additionally, pelvic lymph nodes will be subclassified according to their localization as follows: R/L obturator, R/L external iliac, R/L internal iliac and other (total of 7 subgroups). These regions will not be used for evaluation of the primary or secondary endpoints, but for exploratory analysis.
- ii) Visceral lesions will be considered positive if the ^{68}Ga -PSMA-11 uptake is focal and greater than physiologic background activity of the involvement organ or anatomic site.
 - (1) Visceral lesions will be classified further by major organ: lung, liver, other tissue. These regions will not be used for evaluation of the primary or secondary endpoints, but for exploratory analysis.
- iii) Bone lesions will be considered positive if the ^{68}Ga -PSMA-11 uptake is focal and greater than physiologic bone marrow.
 - (1) Bone lesions will be classified by further by region: spine, ribs, pelvis, extremities, skull, sternum, clavicle. These regions will not be used for evaluation of the primary or secondary endpoints, but for exploratory analysis.
- iv) Prostate bed and prostate lesions will be considered positive if the ^{68}Ga -PSMA-11 uptake is focal and greater than physiologic background activity of the involvement organ or anatomic site.

Reference Standard Definition

b) Follow-up Imaging:

All patients will be followed up 3-12 months with conventional imaging (dedicated CT, MRI and/or bone scan). Interpretation of follow-up imaging will be performed by local read. For lesions that are reported in the blinded reads but not reported in the local evaluation of follow-up imaging, the local readers will be informed of the location of the lesions and follow-up will be performed for these additional lesions. Preferably, the follow-up conventional imaging should be the same modality/modalities as the initial staging work-up to allow for reproducible and accurate comparisons.

^{68}Ga -PSMA-11 PET validation based on follow-up imaging:

- i) Lymph nodes will be assessed by change in size. ^{68}Ga -PSMA-11 positive lymph nodes will be considered:
 - (1) True positive:

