- If there is focal uptake seen in the same location as the PSMA uptake on the baseline bone scan performed within one month of ^{68}Ga -PSMA-11 PET.
- If there is a lesion noted in the same location as the PSMA uptake on the initial MRI performed within one month of ^{68}Ga -PSMA-11 PET.
- If within 12 months follow-up CT demonstrates development of sclerosis in the same location as the PSMA uptake.
- If within 12 months follow-up MRI demonstrates a new bone lesion in the same location as the PSMA uptake.
- If within 12 months follow-up bone scan demonstrates new focal uptake in the same location as the PSMA uptake.
- In subjects with localized suspected bone lesion(s) receiving targeted treatment without concomitant systemic treatment:
 - o If the subject demonstrates a decrease of PSA by greater than 50% after targeted treatment.

(2) False positive:

- In subjects with localized suspected bone lesion(s) receiving targeted treatment without concomitant systemic treatment:
 - o If the subject does not demonstrate a decrease of PSA by greater than 50% after targeted treatment with curative intent (ie non-palliative radiation).
- If ^{68}Ga -PSMA-11 positive bone lesions do not meet the criteria for true positive findings, and appropriate correlative and follow-up imaging was acquired.

(3) If bone lesions do not meet criteria for either true positive or false positive disease listed above, then the patient/region will be considered inevaluable for primary endpoint.

iv) ^{68}Ga -PSMA-11 positive prostate bed and prostate lesions will be considered:

(1) True positive:

- For patients undergoing systemic treatment (alone or in combination with targeted treatment): If on post-treatment follow-up imaging within 3-12 months, lesions seen on CT or MRI decrease by more than 30% in long axis diameter
- In subjects with localized suspected lesions(s) receiving targeted treatment without concomitant systemic treatment there are two ways to meet true positive disease:

- If the subject demonstrates a decrease of PSA by greater than 50% after targeted treatment [OR]
- If on post-treatment follow-up imaging within 3-12 months, lesions seen on CT or MRI decrease by more than 30% in long axis diameter (with a minimum of 3 mm in change in size)

- For untreated patients: If on follow-up imaging within 3-12 months, lesions seen on CT or MRI increase by more than 20% in long axis diameter (with a minimum of 3 mm in change in size).

(2) False positive:

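### Telling local readers where PSMA PET was positive can push the visual follow-up bone calls, and so bone PPV, upward, and the plan does not record which calls were prompted

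*Combined protocol and SAP*

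**What the plan says.** Section 8.1.2 blinds the central PET readers to clinical information and conventional imaging. For the follow-up conventional images it does the reverse: "local readers will be unblinded to all results and will be specifically informed of the location of" PET-positive lesions, "so that follow-up measurements may be performed on these lesions".

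Section 8.3.2, Reference Standard Definition, b) Follow-up Imaging, states "Interpretation of follow-up imaging will be performed by local read". No central, duplicate or blinded read of these images is described. The same paragraph adds a second look. Its trigger is "lesions that are reported in the blinded reads but not reported in the local evaluation of follow-up imaging"; in that case "the local readers will be informed of the location of the lesions and follow-up will be performed for these additional lesions". No matching step is described for sites where PET was negative.

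Node, visceral and prostate-bed lesions are judged under b) i), ii) and iv) mainly by percentage change in diameter, PSA change, or both. Bone, under b) iii), is different. Its follow-up imaging criteria for a true positive are presence-or-absence calls. For CT the wording is "If within 12 months follow-up CT demonstrates development of sclerosis in the same location as the PSMA uptake". MRI and bone scan have matching rules, for a lesion or for focal uptake that is new at the PSMA site. Any one suffices. A PET-positive bone lesion that meets no true-positive criterion, with appropriate imaging acquired, is a false positive.

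Under 8.3.2 d), region-level false negatives come only from pathology. One true-positive region makes the patient true positive unless pathology shows a false positive. A PET-negative patient with biochemical disease counts as a false negative.

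**The concern.** Measuring a node requires knowing which node to measure, so disclosure has a clear purpose for the size-based rules. Deciding whether a follow-up CT, MRI or bone scan shows a new bone finding does not require it. A reader who knows the PSMA site may report an equivocal finding there that would have gone unreported without the prompt.

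The false-positive default makes that visual call decisive: an upgrade takes a lesion out of the false positives and puts it into the PPV numerator. The reference standard for bone is then not independent of the test it is meant to judge. Section 8.2.1 expects biopsy rates to fall and combines imaging with biopsy in the primary aim for that reason, so more will rest on these reads. Section 8.3.2 d) also allows recorded departures from the criteria in individual patients.

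At stake is mainly the credibility of bone PPV. Once a reader knows the sites, the unprompted result cannot be recovered.

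**Working it through.** **Plan figures used.** The documents give no figure for this effect. Section 8.2.1 supplies the scale:
- 75 cases / 0.20 prevalence = 375 patients with follow-up, as stated. A one-sample normal approximation (50% against 70%, one-sided 0.01, 90% power) gives 76.6, close to the stated 75. Nothing below depends on the 75 itself.
- Expected bone share 11%: 0.11 × 375 = 41.25, about 41 men, if that share holds among those with follow-up.
- PET-negative share 24%, so 76% PET-positive. The four region shares sum to 15 + 27 + 24 + 11 = 77, so bone is 11/77 of positives.

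**Assumptions not in the documents.** Bone PPV without prompting, P, is 0.60 to 0.87. The share of would-be false-positive sites upgraded through prompting, u, is 10% to 50%.

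**Bone PPV.** Recorded PPV = P + u(1 − P). Extra true positives = 41.25 × (1 − P) × u.

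| P | u = 10% | u = 25% | u = 50% |
|---|---|---|---|
| 0.60 | 64% (1.7 extra) | 70% (4.1) | 80% (8.2) |
| 0.70 | 73% (1.2) | 77.5% (3.1) | 85% (6.2) |
| 0.87 | 88% (0.5) | 90% (1.3) | 93.5% (2.7) |

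**Bone sensitivity.** This is TP/(TP + FN), with FN from pathology only. Section 8.2.1 reports no false negatives on biopsy in the first cohort. With FN at or near zero the ratio is at or near 100% whatever the TP count, so upgrading barely moves it.

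**Per-patient sensitivity.** Take each PET-positive patient as having one region, all PET-negative patients as false negatives, and P as common to all regions. Sensitivity = 0.76P / (0.76P + 0.24). Bone-only upgrading adds 0.76 × (11/77) × (1 − P) × u to numerator and denominator.
- P = 0.60, u = 50%: 0.456/0.696 = 65.5% becomes 0.4777/0.7177 = 66.6%, up 1.0 point.
- P = 0.70, u = 50%: 0.532/0.772 = 68.9% becomes 0.5483/0.7883 = 69.6%, up 0.6 points.
- P = 0.87, u = 10%: 73.37% becomes 73.41%, up 0.04 points.

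**Would it help to make prompted-only correlates inevaluable?** They would leave the denominator while unmatched sites stay false positive. From P = 0.60:
- u = 25%: 0.60/(0.60 + 0.30) = 66.7%, against 70% when counted. Share of the shift kept: 6.7/10 = 67%.
- u = 50%: 0.60/(0.60 + 0.20) = 75%, against 80%. Share kept: 15/20 = 75%.

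Counting them as not confirmed returns 60% in both cases.

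**The case against.** The strongest reply is that prompting also corrects misses. Section 8.2.1 anticipates conventional-imaging sensitivity of 30-60%, so an unprompted read will overlook real disease and some prompted correlates will be right. That stands: the shift is not all error, and the unprompted figure is a lower bound, not the truth.

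It can also be said that the second look is not wholly one-sided, because a prompted site with appropriate imaging and no correlate is recorded as a false positive. That is correct. But such a site was heading for the same default without the prompt, so prompting at PET-positive sites can change the result only upward.

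Three stronger readings are tempting, and the documents do not support them.
- A reader might infer that bone sensitivity is inflated. Region-level false negatives come only from pathology, so it hardly moves.
- A reader might infer that the 70% success bar is in danger. Starting at 68.9%, 25% upgrading in every region gives 0.589/0.829 = 71.0%, but the other regions rest largely on size and PSA rules, for which disclosure has a purpose. Bone alone adds about 1 point or less, which matters only for a result already close to the bar.
- A reader might infer from 8.3.2 b) that a PET-naive first read exists and is discarded. The text says only that a local evaluation may lack a lesion that the central readers report. It does not say that the local reader was unaware of PET, and under 8.1.2 that reader knows all results. The two passages can be read together: general disclosure, then further disclosure of central-read lesions.

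Scope is limited too. The rule in 8.1.2 concerns follow-up images. The baseline bone criteria have no named reader or blinding rule. The bone criterion based on PSA decline after targeted treatment is unaffected.

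**Conclusion.** The point holds for the visual follow-up bone criteria. Disclosure there goes beyond its stated purpose and, through the false-positive default, pushes bone PPV upward. In the illustration the rise runs from about 1 point (P = 0.87, u = 10%) to 20 points (P = 0.60, u = 50%), or about 0.5 to 8 extra true positives among some 41 men. Those inputs are assumed, and the true size cannot be derived from the documents. The effect on bone sensitivity is likely negligible, and on per-patient sensitivity about 1 point or less from bone alone. This is a worthwhile low-cost improvement to a secondary endpoint and does not undermine the primary one. It has to be set prospectively.

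**What to change.** Amend 8.1.2 and 8.3.2 b) together:
- The local reader records the bone findings on follow-up imaging before the PSMA sites are disclosed for that read. Site matching and size measurement follow, with disclosure kept for them.
- A case-report field marks each bone correlate as reported before disclosure or only after it.
- Bone PPV and per-patient sensitivity are reported two ways. Prompted-only correlates count as true positive (the current rule, upper bound) and as not confirmed, hence false positive under the bone default (lower bound). A lesion that is true positive on another criterion or by pathology stays so in both.
- Prompted-only correlates are not made inevaluable in the main analysis, because that keeps 67-75% of the illustrated shift.
- The plan states who reads the baseline bone criteria and applies the same field to them.

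The cost is a read-order step at each site and one field. The first read may not be fully PET-naive where the PET report is already in the chart, where the CT comes from the PSMA PET itself, or where a site supplies only a report, as section 6.1.3 permits. Such cases should be flagged, since the lower bound is weaker for them.

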8.2 Determination of Sample Size and Accrual Rate

8.2.1 Sample Size and Power Estimate

The primary endpoint is to evaluate the sensitivity on a (1) per-patient and (2) per-region-basis (prostate bed, pelvis, extrapelvic soft tissue, and bone metastases) of ^{68}Ga -PSMA-11 PET for detection of tumor location confirmed by histopathology/biopsy. Based on our first protocol in biochemical recurrent patients, we have updated the distribution of disease that we expect to find:

- a) Prostate bed: 15%
- b) Pelvis: 27%
- c) Extrapelvic soft tissue: 24%
- d) Bone metastases: 11%
- e) No evidence of disease on PSMA PET: 24%

Of our first cohort of patients, 19% of patients underwent biopsy after a positive PSMA PET imaging. Based on biopsy results there was 100% sensitivity and 87% specificity. There were no True Negatives or False Negatives on biopsy. Imaging follow-up is not complete for our first study so we cannot estimate the percent of patients that will have imaging follow-up, but it appears that roughly 15 to 20% of patients will have imaging follow-up. Consistent with our second protocol, we anticipated that the sensitivity for the four regions and for all regions combined using conventional imaging ranges from 30-60%. An overall sensitivity for ^{68}Ga -PSMA-11 PET of at most 50% will be considered as unacceptably low. Hence, the null hypothesis that the sensitivity is at most 50% will be tested against the alternative hypothesis that the sensitivity is greater than 50%. It is hypothesized that ^{68}Ga -PSMA-11 PET imaging on the per-region and per-patient basis will substantially increase the sensitivity for the four regions to at least 70%. A sample size of 75 true positives is required for rejecting the null hypothesis that the sensitivity is at most 50% with 90% power at the one-sided 0.01 ($=0.05/5$ – a Bonferroni adjustment for evaluating the sensitivity for the four regions and for all regions combined) significance level, assuming an average regions specific prevalence of 20%. Although 19% of patients underwent biopsy and 15% of patients have imaging follow-up, we anticipate that the biopsy rate will fall in this study as referring clinicians become more comfortable with the imaging results. Therefore, we will combine imaging and biopsy follow-up in the primary aim, and will require 375 with both imaging and/or biopsy follow-up in order to power the analysis at a per region level. Assuming a prevalence rate of 20% for disease in each individual region, a total sample size of 1,500 patients is required. In summary, the proposed target accrual of 1,500 patients (375 with biopsies or imaging follow-up) will provide adequate power for detecting the anticipated improvement in the sensitivity for both the per-patient and per-region based ^{68}Ga -PSMA-11 PET imaging. However, a sample size of 107 patients with biopsies/follow-up in total is sufficient for detecting the anticipated improvement in sensitivity when evaluating per-patient based sensitivity.

Our current biochemical recurrence protocol has not completed analysis or enrollment. Therefore we will perform an analysis of our first protocol and based on those results we may adjust the sample size of this protocol using updated assumptions based on the interim analysis of our existing protocol.

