 - For patients undergoing systemic treatment (alone or in combination with targeted treatment): If on post-treatment follow-up imaging within 3-12 months, lymph nodes seen on CT or MRI decrease by more than 30% in short axis diameter and PSA declines by more than 50%.

- If PSA increases by more than 50% on systemic therapy, then a increase in the size of lesion by more than 20% will be considered a true positive lesion.
- In subjects with localized suspected lymph node(s) receiving targeted treatment without concomitant systemic treatment there are two ways to meet true positive disease:
- If the subject shows a decrease of PSA by greater than 50% after targeted treatment and the lymph node does not enlarge (change in size less than 20% or less than 3 mm increase in short axis diameter) [OR]
 - If on post-treatment follow-up imaging within 3-12 months, lymph nodes seen on CT or MRI decrease by more than 30% in short axis diameter (with a minimum of 3 mm in change in size)
- For untreated patients: If on follow-up imaging within 3-12 months, lymph nodes seen on CT or MRI increase by more than 20% in short axis diameter (with a minimum of 3 mm in change in size).
- (2) False positive:
- For patients undergoing systemic treatment (alone or in combination with targeted treatment): If on post-treatment follow-up imaging within 3-12 months, lymph nodes seen on CT or MRI increase by more than 20% in short axis diameter and PSA decreases by more than 50%.
- In subjects with localized suspected lymph node(s) receiving targeted treatment without concomitant systemic treatment there are two ways to meet false positive disease:
- If the subject does not demonstrate a decrease of PSA by greater than 50% after targeted treatment [OR]
 - If on post-treatment follow-up imaging within 3-12 months, lymph nodes seen on CT or MRI increase by more than 20% in short axis diameter (with a minimum of 3 mm in change in size)
- For untreated patients: If on follow-up imaging within 3-12 months, lymph nodes seen on CT or MRI decrease by more than 30% in short axis diameter (with a minimum of 3 mm in change in size).
- (3) If all regions in a patient/region do not meet criteria for either True positive or False positive disease, then the patient/region will be considered inevaluable for primary endpoint.
- ii) Visceral lesions (non-lymph node soft tissue or organ) will be assessed by change in size. ⁶⁸Ga-PSMA-11 positive visceral lesions will be considered:
- (1) True positive:

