- (2) True negative patient: in the absence of True Positive or False Positive lesions, a patient will be considered a True Negative if there is pathology that is negative for disease and corresponding lesion is negative by PSMA PET.
 - (3) False positive patient:
 - (a) Pathology confirms a false positive lesion that is read as positive on PSMA PET.
 - (b) In the absence of pathology: there are no true positive regions, and there is a region that is categorized as false positive based on imaging or clinical follow-up.
 - (4) False negative patient: in the absence of True Positive or False Positive lesions, a patient will be considered a False Negative if there is pathology that is positive for disease and corresponding lesion is negative by PSMA PET. Additionally, patients without evidence of disease on PSMA PET but with biochemical evidence of disease will be considered a False Negative.
- ii) Region level evaluation: Each patient will have four evaluable regions (Table 1: prostate bed, pelvis, extrapelvic soft tissue, and bone metastases). Each region will be categorized as true positive or false positive as described above. Regions without evidence of PSMA positive disease or deemed inevaluable will not be included in the analysis.
 - (1) True positive region:
 - (a) Pathology confirms a PSMA avid lesion as a true positive in the region.
 - (b) In the absence of pathology, clinical or imaging follow-up demonstrates a true positive lesion within the region independent of the presence of an inevaluable lesion or a false positive lesion
 - ie true positive disease will supersede a false positive lesion in the region based analysis if based on imaging/clinical follow-up
 - (2) True negative region: in the absence of True Positive or False Positive lesions within a region, the region will be considered a True Negative if there is pathology that is negative for disease in the region and corresponding lesion is negative by PSMA PET.
 - (3) False positive region:
 - (a) Pathology confirms a PSMA avid lesion as a false positive in the region

- (b) In the absence of pathology, there are no true positive lesions in the region, and there is a false positive lesion by clinical or imaging follow-up.
- (4) False negative region: in the absence of True Positive or False Positive lesions in a region, the region will be considered a False Negative if there is pathology that is positive for disease in the region and corresponding lesion is negative by PSMA PET.

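### The follow-up target of 375 patients is exactly 75/0.20, with no allowance for inevaluable cases, so the stated 90% per-region power is not secured

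*Combined protocol and SAP*

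**What the plan says.** Section 8.2.1 sets up one test per region and one for all regions combined: "the null hypothesis that the sensitivity is at most 50% will be tested against the alternative hypothesis" of a sensitivity above 50%. It expects that PET "will substantially increase the sensitivity for the four regions to at least 70" per cent. The case count is given as "A sample size of 75 true positives is required for rejecting the null hypothesis", "with 90% power at the one-sided 0.01" level (0.05/5).

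The step from cases to patients is that the trial "will require 375 with both imaging and/or biopsy follow-up in order to power the analysis at a per region level". Total enrolment follows: "Assuming a prevalence rate of 20% for disease in each individual region, a total sample size of 1,500 patients is required". For the per-patient analysis, the same section says 107 patients with biopsy or follow-up are enough.

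Section 8.3.2 b) creates an inevaluable class. For nodes, visceral lesions and bone, if neither set of criteria is met, "then the patient/region will be considered inevaluable for primary endpoint". For the prostate bed, it is the lesion that becomes inevaluable. Section 8.3.2 d) ii) adds: "Regions without evidence of PSMA positive disease or deemed inevaluable will not be included in the analysis".

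**The concern.** Being followed is not the same as being classifiable. An untreated node that changes little in size over 3 to 12 months has follow-up but meets neither rule. So does a node or visceral lesion under systemic treatment that misses the joint size and PSA thresholds. Such a patient counts towards the 375 but may add nothing to the per-region analysis.

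The 90% power belongs to the cases that enter the analysis. A team that counts to 375 followed patients and stops could report per-region power that it does not have, in a dataset that Section 1.1 intends for a marketing application.

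**Working it through.** **Inputs from Section 8.2.1:** null sensitivity 0.50; alternative 0.70; one-sided alpha 0.01; power 0.90; 75 cases; prevalence 20% in each region; 375 followed; 1,500 enrolled. **Input not in the documents:** the inevaluable share d, taken here as 0% to 50%.

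**1. Reproduce the 75.** One-sample proportion, normal approximation:

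n = (z0.99·√(0.5·0.5) + z0.90·√(0.7·0.3))² / 0.2² = (2.326·0.5 + 1.282·0.458)² / 0.04 = 76.6.

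This is within two of the plan's 75. The 75 works as the number of reference-positive cases (true positives plus false negatives), although the plan calls them true positives.

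Power at n = Φ((0.2·√n − 2.326·0.5)/0.458). At n = 75 this is Φ(1.24) = 0.893, so the plan's figure is reproduced to rounding.

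**2. Reproduce the 375.** 75/0.20 = 375 and 375/1,500 = 25%. Nothing is added for loss.

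**3. Power when exactly 375 are followed.** Cases = 75·(1 − d), rounded down. The exact test rejects at the smallest count whose size does not exceed 0.01.

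| Inevaluable (assumed) | Cases | Normal approximation | Exact: reject at | Exact power |
|---|---|---|---|---|
| 0% | 75 | 0.89 | 49 or more | 0.84 |
| 10% | 67 | 0.85 | 44 or more | 0.82 |
| 20% | 60 | 0.80 | 40 or more | 0.76 |
| 30% | 52 | 0.73 | 35 or more | 0.72 |
| 50% | 37 | 0.55 | 27 or more | 0.42 |

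The exact figures move unevenly because the count is discrete, and at 50% loss they fall well below the approximation. At 75 cases exact power is already under 0.90, so there is no hidden reserve.

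**4. Followed patients needed to keep 75 cases at 20% prevalence.** 375/(1 − d): 417 at 10%, 469 at 20%, 536 at 30%, 750 at 50%.

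**5. The plan's own regional shares, no loss.** Section 8.2.1 lists expected findings of 15%, 27%, 24% and 11%. Read as prevalences:

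| Region | Cases in 375 | Power (normal approximation) | Loss tolerated, 1 − 75/cases |
|---|---|---|---|
| Prostate bed | 375·0.15 = 56 | 0.77 | none; short of 75 already |
| Pelvis | 375·0.27 = 101 | 0.97 | 26% |
| Extrapelvic soft tissue | 375·0.24 = 90 | 0.945 | 17% |
| Bone | 375·0.11 = 41 | 0.60 | none; short of 75 already |

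These shares are PET findings. With the 24% PET-negative group they sum to 101%, so they look like exclusive categories, and true prevalence per region may be higher.

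**6. How many might be followed.** Section 8.2.1 reports 19% biopsied and 15% with imaging follow-up. Without overlap that is 0.34·1,500 = 510; with full overlap it is 0.19·1,500 = 285. A total of 510 would leave 375 after a loss of 1 − 375/510 = 26%.

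**The case against.** The strongest reply is that 375 is a required yield, not a forecast, and can be read as patients with a usable reference standard. At the rates in Section 8.2.1, 1,500 patients could supply up to 510 with follow-up. Section 8.3.2 b) says that all patients will have follow-up imaging, and Section 8.2.1 allows the sample size to be adjusted after the first protocol is analysed.

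Part of this stands: more than 375 may be followed, which would absorb some loss. But 510 requires no overlap, the plan itself expects the biopsy rate to fall, and it sizes on roughly 15 to 20% with imaging follow-up rather than on all patients. The re-sizing clause is optional and names no evaluability input. No surplus is presented as a margin, and Section 8.2.1 never mentions evaluability when it describes the 375.

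The inevaluable rules also differ by site and treatment, so a flat loss rate is only a device:

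- A bone lesion that fails the true-positive criteria counts as false positive if appropriate imaging was acquired. It is then classified, although a false positive does not add to a sensitivity count.
- In the prostate bed, the lesion rather than the patient or region is inevaluable.
- With targeted treatment only, PSA alone settles most cases.
- Pathology classifies regardless of size change.

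A reader might infer that 75 cases are reached only if nobody is inevaluable. That holds only at a uniform 20% prevalence. On the plan's shares, zero loss is not needed for pelvis and extrapelvic tissue, and does not suffice for prostate bed and bone.

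**Conclusion.** The concern holds in a limited form. Under the plan's uniform 20% prevalence, 375 followed patients give exactly 75 cases per region, with nothing set aside for the cases that Section 8.3.2 excludes. If only 375 are followed, the 90% per-region power is not secured: about 0.85 at 10% loss and 0.80 at 20% by the normal approximation, or 0.82 and 0.76 by the exact test.

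A reader might go further and conclude that the power will not be delivered. The documents do not support that, because they give no inevaluable rate and more than 375 patients may be followed. Nor is inevaluability the largest threat in every region: if the listed shares are prevalences, prostate bed and bone fall short before any loss.

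Per-patient power is not threatened by modest loss, since the plan needs 107 and half of 375 is still 187.

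**What to change.** In Section 8.2.1:

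- State the requirement for 90% per-region power as 75 evaluable reference-positive cases in each region under Section 8.3.2 d), in place of 375 patients with follow-up. Redefining the 375 as evaluable patients would not be enough. A PET-negative patient with biochemical disease is an evaluable false negative at patient level but adds no regional case without pathology.
- Track that count by region during the trial.
- State that 90% power with 375 followed patients assumes 20% prevalence in every region and no inevaluable cases. Give the power at 10% to 50% loss and at the listed regional shares (prostate bed about 56 cases, 0.77; bone about 41, 0.60, if the shares are prevalences).

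The cost is wording and one tracked count per region. The stated per-region power becomes less favourable. The change itself adds no patients, procedures or readers; where a region stays below 75, the power claimed for that region is what gives way.
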